2.7 Sample size calculation

We calculate the sample size by using the following formula [5]:

$$n = 21 \cdot \frac{\sigma^2}{d^2} = 21 \cdot \frac{8^2}{4^2} \approx 84 \text{ patients}$$

[n = number of subjects σ = standard deviation d = relevant difference $\alpha = 0,05$ $\beta = 0,10$] [6]

With a follow-up period of 5 years on average, we expect a response rate of 65%. Therefore the sample size will be 130 ($n = 84 / 0.65 \approx 130$ patients)

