2. SYNOPSIS

2.1 Study objective

We designed this study to assess the long-term outcome after implantation of the supraciliary CyPass microstent beyond two years. The long-term results are of considerable importance for the evaluation and positioning of the CyPass stent procedure in the surgical glaucoma treatment armamentarium. We will collect data of a follow-up period of an average of 5 years.

The main research outcome is the determination of the efficacy of CyPass microstent implantation in reducing the intraocular pressure, the number of necessary antiglaucomatous medications and the progression of glaucoma in terms of visual field worsening and progression of glaucomatous optic disc changes.

Another main outcome is the safety of the procedure based on the intraoperative and postoperative complications.

Secondary outcomes include the development of the stent-associated blebs, the long-term success rate of the CyPass stent, and the clinical identification of stent failures.

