2.2 Study population

- We plan to examine at least 84 eyes. Therefore, we invite patients with at least 130 study eyes (see sample size calculation 2.7).
- All patients after implantation of a CyPass microstent on at least one eye. Excluded are patients which had combined operation (phacoemulsification with intraocular lens implantation and CyPass stent implantation)
- We will not invite the patients of whom we already have the long-term data available because they had been examined in the past at the department of Ophthalmology. We will take the available data from the medical records.
- Patients with secondary surgery due to CyPass failure will not be invited for the examination. We will collect the available data up to the date of the new operation from the patient's records and classify these cases as failure.

Protocol Version II 5-year CyPass results

- The following inclusion and exclusion criteria are considered for the prospective part of the study:

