2.3 Study design

Monocentric study with two parts:

- Retrospective part: Collection of preoperative, intraoperative and postoperative data from the medical records
- Prospective part: Inviting patients according to inclusion and exclusion criteria for a single examination and collection of postoperative data after an average of five years

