5. STATISTICAL EVALUATION

For data protection reasons, all data of a patient are immediately pseudonymised after completing the data collection. The study assistant ensures that it is no longer possible to draw any conclusions about the respective patient from the data collected.

The data is statistically evaluated with the computer program STATISTICA (Version 10, StatSoft GmbH, Hamburg, Germany) using adequate statistical procedures.

Classification of the Follow-up-Visits according to the examination timeframe recommended by the WGA (World Glaucoma Association) [11]:

	D1	W1	M1	M3	M6	M12	M18	M24	M36
Ideal	1 day	7 days	28-31 days	90-92 days	181-183 days	yearly Date	547-548 days	yearly Date	yearly Date
Preferred	1-2 days	4-11 days	21-42 days	77-106 days	161-204 days	334-387 days	486-609 days	669-822 days	±91 days
Acceptable	1-3 days	4-14 days	15-60 days	61-122 days	123-272 days	273-456 days	457-639 days	640-913 days	± 181 days

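### Section 2.7 sizes each of two independent groups, but the study is one cohort measured before and after surgery, and its 84 is counted as patients in section 2.7 and as eyes in section 2.2

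*Combined protocol and SAP*

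**What the plan says.** Section 2.7 opens with "We calculate the sample size by using the following formula" and gives n = 21·8²/4² = 84 patients, at α = 0.05 and β = 0.10. The only key to the symbols is "n = number of subjects σ = standard deviation d = relevant difference". It then divides 84 by an expected response rate of 65% and reports 130 patients. It states no outcome, unit of measurement, test, number of groups or sidedness.

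Section 2.2 uses the same two figures with a different unit: "We plan to examine at least 84 eyes. Therefore, we invite patients with at least 130 study eyes (see sample size calculation 2.7". It describes the population as "All patients after implantation of a CyPass microstent on at least one eye", so one patient may contribute two eyes.

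Section 2.1 lists several main outcomes, beginning with "efficacy of CyPass microstent implantation in reducing the intraocular pressure, the number of necessary antiglaucomatous medications" and going on to progression and safety. Section 2.3 describes retrospective collection of pre-, intra- and postoperative data, and a prospective part: "Inviting patients according to inclusion and exclusion criteria for a single examination and collection of postoperative data after an average of five years". Section 3 says that all potential participants received the stent. Section 5 says only that the data are evaluated "using adequate statistical procedures".

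**The concern.** The constant in a sample size formula shows which comparison it was built for, and 21 points to two independent groups. This study has no second group; the subgroups in section 2.6 are outcome categories, not comparison arms. If the main question is how far values fall from before surgery to about five years later, the relevant quantity is the SD of the within-subject change. Section 2.7 does not say whether 8 is that SD or the SD of single values.

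At stake is whether the 90% power means anything for this study. As written, a reader cannot tell for which outcome, or on what scale, a difference of 4 is detectable. The change of unit adds to this. Two eyes of one patient are usually correlated, so 84 eyes carry less information than 84 patients. The loss depends on the number of patients with two study eyes and on the between-eye correlation, and the plan gives neither.

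**Working it through.** **Inputs from section 2.7.** σ = 8, d = 4, α = 0.05, β = 0.10, response rate 65%.

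**Reproducing the plan's figures.** 21 × 64/16 = 84, and 84/0.65 = 129.2, so 130. Both are right.

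**What the constant is.** With z_0.975 = 1.960 and z_0.90 = 1.2816:

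- two independent means, two-sided, per group: 2(1.960 + 1.2816)² = 21.01
- two independent means, one-sided: 17.13
- one-sample or paired, two-sided: 10.51
- one-sample or paired, one-sided: 8.56

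Only the first gives 21. The stated 90% power is therefore that of 84 against 84, or 168 subjects in all.

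**Paired comparison, 84 independent patients, 8 taken as the SD of change.** n = 10.507 × 64/16 = 42.03, so 43. By the t distribution, power is 0.893 at 43 and 0.900 at 44, so 44. With n = 84, power for a difference of 4 is 99.5%, the difference detectable with 90% power is 2.9, and the 95% CI half-width is t_0.975,83 × 8/√84 = 1.7.

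**Paired comparison, 8 taken as the SD of single values.** SD of change = 8√(2(1 − ρ)), where ρ is the pre-post correlation, so n = 84.06(1 − ρ). The documents give no ρ; the range is assumed.

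| ρ | SD of change | n needed, normal (t) | power at 84, by t |
|---|---|---|---|
| 0 | 11.31 | 85 (87) | 89.3% |
| 0.3 | 9.47 | 59 (61) | 96.9% |
| 0.5 | 8.00 | 43 (44) | 99.5% |
| 0.7 | 6.20 | 26 (28) | >99.9% |

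By the normal formula, power at ρ = 0 is 90.0%. With 84 patients, power drops below 90% only when the SD of change exceeds 11.3 (11.2 by t, which corresponds to ρ below about 0.02).

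**84 eyes.** Let k be the number of patients with two study eyes and ICC the between-eye correlation of the changes. The design effect is 1 + (2k/84) × ICC. Neither quantity is in the documents. I assumed that 10% to 50% of patients contribute both eyes and that the ICC is 0.3 to 0.7, and show the two ends.

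| | 10% with two eyes, ICC 0.3 | 50% with two eyes, ICC 0.7 |
|---|---|---|
| Patients | 84/1.1 = 76.4 | 84/1.5 = 56 |
| k | 7.6 | 28 |
| Design effect | 1.055 | 1.467 |
| Equivalent independent patients | 79.7 | 57.3 |
| Power, SD of change 8 | 99.3% | 96.1% |
| Detectable difference, SD of change 8 | 2.9 | 3.5 |
| 95% CI half-width, SD of change 8 | 1.8 | 2.1 |
| Power, SD of change 11.3 (ρ = 0) | 88% | 75% |
| Smallest ρ for 90% power, single-value SD 8 | 0.08 | 0.34 |

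**The case against.** The strongest reply is that the printed formula coincides with a paired calculation that takes no credit for pre-post correlation: with σ as the SD of single values, the paired n is 21.01(1 − ρ)σ²/d², and at ρ = 0 that is section 2.7. For independent patients the plan then errs on the safe side. This stands, and the point is not that the study is underpowered. But section 2.7 does not say it made that choice, and the coincidence disappears if 8 is the SD of change.

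Section 2.7 does state d, σ, α and β. What is missing is the outcome, the unit and the type of SD, and without these the four numbers cannot be interpreted. The sources cited there may explain 8 and 4, but the plan does not repeat that explanation.

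The before-after comparison is inferred, since section 5 names no test. The inference rests on the stated aim and the data collected; no passage describes a second group.

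The low powers for eyes stack assumptions. The 75% figure takes zero pre-post correlation together with the unfavourable ends of two assumed ranges, and section 2.2 permits two-eye patients without saying how many there are. These figures are a sensitivity range, not evidence of a shortfall. The targets are also minima, and section 2.2 adds record data from patients who are not invited, without saying whether their eyes count towards the 84.

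Finally, correcting the sample size for two eyes does not make the analysis valid unless section 5 also handles them. That is right, and the fix includes it.

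**Conclusion.** The concern holds. The arithmetic in section 2.7 is correct, but the formula gives the size of each of two independent groups in a study that has one. The stated 90% power is therefore not the power of this design, and sections 2.7 and 2.2 disagree on what is being counted.

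For independent patients the consequence is mild: 84 gives between 89.3% power (single-value SD 8, ρ = 0, by t) and 99.5% (SD of change 8), and more at higher correlations. That reassurance weakens if the 84 are eyes, because the margin then depends on the share of two-eye patients and the between-eye correlation. Under the assumed ranges, power stays at 96% or more with SD of change 8 but falls to between 88% and 75% with SD of change 11.3.

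All of this assumes a two-sided paired comparison of means. The restatement should be made; nothing here shows that the study is too small.

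**What to change.** 1. In section 2.7, name the outcome, its unit, the test and its sidedness. For a before-after comparison of means, use n = (z_0.975 + z_0.90)² × SD_change²/d².
2. State whether 8 is the SD of the change or of single values. If the latter, give the assumed pre-post correlation and convert it with SD_change = 8√(2(1 − ρ)).
3. Choose patients or eyes as the counting unit, and use it for both 84 and 130 in sections 2.2 and 2.7.
4. If eyes are the unit, give the expected number k of patients with two study eyes and an assumed between-eye correlation, and divide 84 by 1 + (2k/84) × ICC to get the number of independent patients it is worth. Add a sentence to section 5 on how two eyes of one patient are analysed.
5. The target of 84 can stay. After steps 1 to 4, report the power, detectable difference or CI half-width it gives. The figures 99.5%, 2.9 and 1.7 may be used only for 84 independent patients with SD of change 8.

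The cost is a rewording of section 2.7 and one line of section 2.2, with a sentence in section 5 if eyes are counted. No added patients are needed.

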3. OBSERVATION PERIOD

All patients potentially taking part in the study were treated with a CyPass micro-stent at the Department of Ophthalmology in Neubrandenburg between 2009 and 2014. Thus, we know the exact date of operation.

The duration of the observation period for each patient depends on the duration of the postoperative period up to the last follow-up visit in the Department of Ophthalmology Neubrandenburg in the context of the study. With follow-up visits, scheduled for the second half of 2016, we expect an average follow-up of more than five years.

4. Procedure

4.1 Screening

All patients who underwent CyPass microstent implantation without combination with cataract surgery, in the period between 2009 and the end of 2014 are potential candidates for the study. The selection of patients takes place according to the inclusion and exclusion criteria. Once a patient has met the criteria described above, we inform him in written form or by telephone about the study and ask him to participate.

4.2 Patient recruitment

The patient participates in the study when he fulfills the inclusion and exclusion criteria based on the findings and when he has signed the informed consent. We take out a proband insurance and travel insurance before the start of the study.

4.3 Patient pseudonymisation

After completion of the data collection, every patient record is provided with a unique patient identification code (pseudonymisation). This code is for study purposes only. After data collection, only the study physician and the study assistant can identify the patient.

4.4 Documentation

The data will be collected first via a data collection form (Appendix 1) and then via the Excel program. We collect the intraoperative information from the surgical documentation books, the surgical reports and the patient medical records.

- Surgery-Date
- Patient Name, date of birth, gender and address of the patient
- Operated eye (OD/OS)
- Anesthesia
- Intraoperative course, peculiarities or complications
- Preoperative findings
- Postoperative findings

4.5 Postoperative data collection

We collect the following data prospectively (at the five-year follow-up visit):

- i. *Intermediate history:* First, asking the patients about the postoperative course and the regular check-ups at the registered ophthalmologist. If available, taking the intermediate eye pressure values and the course of the topical therapy, which may have been documented by the Glaucoma pass. Documentation of events such as bleeding or acute IOP-increase. Also documentation of intermediate treatments with date, if any, such as laser treatments.

ii. *Intraocular pressure:* Measuring the intraocular pressure twice in a row using a properly calibrated Goldmann tonometer (Carl Zeiss Meditec, Jena, Germany). The measurements should take place at the same time (± 1 hour) as preoperatively. Documentation of the average value of both measurements is required. If there is a difference of more than three mmHg between these two measurements, a third measurement is taken and the average of all three measurements is documented. The physician doctor measure the intraocular pressure and the assistant reads it. The target pressure is determined according to the criteria of WGA (World Glaucoma Association) [7]. We initially classify the patients into three groups according to visual field damage (mean deviation):

- mild damage (> -5 dB to -10 dB): target IOP ≤ 21 mmHg and IOP reduction $\geq 20\%$
- moderate damage (> -10 dB to -15 dB): target IOP ≤ 18 mmHg and IOP reduction $\geq 30\%$
- severe damage (> -15 dB): target IOP ≤ 15 mmHg and IOP reduction $\geq 40\%$

iii. *Central corneal thickness:* A corneal topography is performed using Visante OCT (Model: 1000, Carl Zeiss Meditec, Jena, Germany). We define the thinnest part of the cornea as central corneal thickness. Alternatively, if the Visante OCT topography is not available (e.g., blepharospasm), three measurements are taken by means of an ultrasonic pachymeter (OcuScan, Alcon, Fort Worth, Texas, USA) to determine the central corneal thickness. The average of these three measurements is considered central corneal thickness.

iv. *Visual field:* The visual field examination is performed by using the Humphrey Perimeter (Humphrey Field Analyzer, Model 720i, Carl Zeiss Meditec, Jena, Germany) with threshold test centrally 24-2. The visual field is evaluated with the help of the MD value and the PSD value. The rate of progression is expressed in the form of dB / year [8]. As a significant clinical change (improvement or worsening), MD values of ≥ 3 decibels are assessed [9]. In addition, the visual field defects in the central 5-degree visual field are counted in all four quadrants (4 visual field points in total) and evaluated as follows: points with sensitivity level > 10 dB are classified with 0 point, while the points with ≤ 10 dB are evaluated with 1 point. The points are added and then divided by 4. Thus, in the evaluation, the normal regular central visual field will be rated with 0 and the advanced central scotoma in all four quadrants is rated as 1.0.

v. *Glaucoma therapy:* Number and name of the active ingredients of the prescribed topical and systemic antiglaucomatous medications preoperatively and at follow-up visits are assessed. The duration of the postoperative drug-free phase is documented. The systemic intake of acetazolamide (carbonic anhydrase inhibitor) is documented separately and evaluated as absolute failure.

vi. *Visual acuity:* First, the refraction is measured with an auto refractometer (KR-800S, Topcon, Tokyo, Japan). The best-corrected visual acuity is checked and adjusted with the best possible correction using Snellen chart. For the statistical evaluation, a visual acuity of hand motion is documented as 1/800, light perception as 1/1600, and Nulla-lux as 1/3200 [10].

vii. *The optic disc change:* Pre- and postoperative optic disc measurement is performed using the HRT II (Heidelberg Retina Tomograph II, Heidelberg Engineering GmbH, Heidelberg, Germany). The area of the optic disc and

the course of the rim area changes are documented and evaluated. Furthermore, the disc change is assessed and evaluated with the help of MRA (Moorfields Regression Analysis). The entire disc area is divided into 6 segments. First, the green segments lying within the standard range are rated with 0 points. The borderline yellow segments are scored 1 point and the pathologic red segments are scored with 2 points. The total number of points is added and then divided by 12. That means the normal non-glaucomatous papilla is rated with 0, the optic disc with terminal damage by glaucoma in all segments rated with 1.0.

viii. *The nerve fiber layer:* A measurement of the thickness of the peripapillary nerve fiber layer is carried out by the Stratus OCT (Model 3000, Carl Zeiss Meditec, Jena, Germany). The evaluation of nerve fibers is performed according to the number of damaged segments and the extent of damage of each segment. Each measurement results in 12 segments. The healthy segments (shown in green) are classified with 0 points, the moderately damaged segments (shown in yellow) are classified with 1 point and the markedly damaged segments in red are classified with 2 points. The total number of points is added and divided by 12, resulting in an average number of evaluable segments. The numbers of non-evaluable segments (shown in white), if any, are subtracted from the 12 segments and the total score is then divided by the number of segments that can be evaluated.

ix. *Description of the CyPass stent and the bleb:* By using the Visante OCT (Model: 1000, Carl Zeiss Meditec, Jena, Germany) the stent and the stent-associated bleb are morphologically visualized. It is assessed if the stent lumen is clear or if there is a CyPass occlusion. The size of the bleb is assessed and classified morphologically into 4 groups. While the largest bleb is assessed with 3 points, the absence of the bleb is rated with 0 points.

x. *Position of the stent:* The stent position is assessed by a gonioscopic examination of the angle of the anterior chamber with the Goldmann goniolens. Possible iris tissue growing and anomalies of the neighboring tissue (goniosynechiae) are documented as follows:

- If there are no synechiae, it is classified with 0 points.
- Goniosynechiae around the stent but without collar or lumen involvement are classified with 1 point.
- Collar and / or lumen involvement of goniosynechiae is classified as 2 points.
- Completely overgrown and closed CyPass stent is classified with 3 points.

The depth of CyPass implantation is also assessed and documented using the number of visible rings. If the stent is not visible, it is rated with 0 points, if only the collar is visible, it is rated with 0.5 points. Depending on the number of rings visible, 1 to 3 points (one point per ring) are given.

New findings will be added to the data collection table in the Excel program.

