2.6 Success of the treatment

We use two classifications to define treatment success:

- The first classification: dividing patients into 2 groups according to the need for postoperative glaucomatous medication: with and without medication. Then we divide each group into 4 subgroups according to the postoperative intraocular pressure achieved: patients with $IOP > 21\text{mmHg}$, patients with $IOP \leq 21\text{mmHg}$ and $> 18\text{mmHg}$, patients with $IOP \leq 18\text{mmHg}$ and $> 15\text{mmHg}$, and patients with $IOP \leq 15\text{mmHg}$.
- The second classification: definition of the treatment success according to the criteria of WGA (World Glaucoma Association) [4]. Complete success is achieved if the target IOP is reached without additional medication. Achieving the target pressure with additional local therapy is rated as qualified success. The loss of visual acuity to 'nulla lux' because of glaucoma progression, the need for systemic therapy with CAI (carbonic anhydrase inhibitor) to reduce pressure or the need for second glaucoma surgery are classified as complete failures.

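### The mean-deviation bands that set the target IOP fail as printed; read by size of loss, eyes with a loss of 5 dB or less have no printed target and no printed route to success

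*Combined protocol and SAP*

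**What the plan says.** Section 2.6 defines two success classifications. The first uses medication status and fixed IOP cut-offs of 21, 18 and 15 mmHg. The second depends on a target: "Complete success is achieved if the target IOP is reached without additional medication", and "Achieving the target pressure with additional local therapy is rated as qualified success". Complete failure in the second classification needs no target. It follows from nulla lux through glaucoma progression, systemic carbonic anhydrase inhibitor (CAI) therapy, or a second glaucoma operation.

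The target comes from section 4.5, item ii: "The target pressure is determined according to the criteria of WGA (World Glaucoma Association) [7", followed by "We initially classify the patients into three groups according to visual field damage (mean deviation". The three groups are:

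- "mild damage (> -5 dB to -10 dB"): at most 21 mmHg and a reduction of at least 20%
- "moderate damage (> -10 dB to -15 dB"): at most 18 mmHg and at least 30%
- "severe damage (> -15 dB"): at most 15 mmHg and at least 40%

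No other section prints a target. Section 2.2 and the inclusion and exclusion criteria set no visual-field limit, and section 4.1 makes all stand-alone implantations from 2009 to 2014 potential candidates. Re-operated patients are handled from records: "Patients with secondary surgery due to CyPass failure will not be invited for the examination", and section 2.2 counts them as failures.

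**The concern.** A success rule must give every eligible eye an outcome. Here some eyes have no printed target, whichever way the bands are read. Under the size-of-loss reading, these are the eyes with the least field damage. Such an eye can be a complete failure through systemic CAI or second glaucoma surgery, or through nulla lux if the preoperative MD sets the band. No printed rule lets it be a complete or qualified success.

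The analyst must then count these eyes as non-successes (which biases the rate downward), leave them out (so that the rate no longer describes the mildest eyes), or choose a target when the IOP is already known. The long-term success rate is a named secondary outcome in section 2.1.

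The MD that sets the band is also unspecified. The bands stand in the section on data collected at the five-year visit, but the target could equally rest on the preoperative field. If the five-year MD were used, progression, which is itself an outcome, could change an eye's own target.

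**Working it through.** **Inputs.** Band limits and targets are from section 4.5 ii, the 3 dB change criterion from 4.5 iv, and the success rules from 2.6. The figure of 84 eyes is from 2.2 and 2.7 (21 × 8² / 4² = 84) and serves only as an illustrative denominator. The plan gives no figure of its own for the share of eyes in each band.

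**Step 1: apply the bands under both readings.** As signed numbers, mild means MD > -5 and MD ≤ -10, which no value satisfies. Moderate means MD > -10 and MD ≤ -15, also impossible. Severe means MD > -15. By size of loss (loss = -MD), mild is 5 < loss ≤ 10, moderate is 10 < loss ≤ 15, and severe is loss > 15.

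| MD (dB) | Signed, as printed | By size of loss |
|---|---|---|
| 0 | severe | none |
| -2 | severe | none |
| -5 | severe | none |
| -8 | severe | mild |
| -12 | severe | moderate |
| -15 | none | moderate |
| -20 | none | severe |

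Only the second reading gives distinct, ordered groups, and it leaves out every eye with a loss of 5 dB or less.

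**Step 2: one eye, three MD values (assumed example, size-of-loss reading).** IOP falls from 24 to 19 mmHg without medication, a reduction of (24 - 19)/24 = 20.8%.

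- MD -8 dB: 19 ≤ 21 and 20.8% ≥ 20%, so complete success.
- MD -11 dB: the target is ≤ 18 mmHg and ≥ 30%, that is ≤ 24 × 0.70 = 16.8 mmHg, so it is missed.
- MD -4 dB: no printed target, so success cannot be assessed.

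**Step 3: effect of using the five-year MD.** A worsening of 3 dB carries an eye across the next limit if its loss was >2 to 5 dB (no band to mild), >7 to 10 dB (mild to moderate) or >12 to 15 dB (moderate to severe). The first group acquires a target only by progressing.

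**Step 4: how many eyes might be in the gap.** The documents do not say. As an illustration, assume a normal MD truncated at 0 dB, with mean μ from -12 to -6 dB and SD σ from 6 to 8 dB before truncation:

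share = [Φ((0 - μ)/σ) - Φ((-5 - μ)/σ)] / Φ((0 - μ)/σ)

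| μ, σ | Share with loss ≤ 5 dB |
|---|---|
| -6, 6 | 32.7% |
| -6, 8 | 28.9% |
| -8, 7 | 23.8% |
| -10, 8 | 17.9% |
| -12, 8 | 13.3% |
| -12, 6 | 10.1% |

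Over the whole grid the share runs from 10.1% to 32.7%; times 84, that is 8.5 to 27.5 eyes. Without truncation it runs from 12.2% to 45.0%, but the distributions with mean -6 dB place 15.9% (SD 6) to 22.7% (SD 8) of eyes above 0 dB. Under the signed reading, the truncated model leaves 7.9% (-6, 6) to 37.9% (-12, 8) of eyes, those at -15 dB or worse, without a target.

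**The case against.** The strongest reply is that the defect is one of notation. The labels and the progressively tighter targets point to size of loss, and no analyst would apply the signed reading. That is fair, but correcting the signs alone does not close the gap at 5 dB.

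Second, the target is taken by reference from a cited guideline that may cover these eyes, and the plan speaks of putting the patients into three groups, as if everyone belonged to one. This stands as a limit: what can be shown is that no target is printed, not that none exists in the source. It also means the investigators may be able to settle the point quickly.

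Third, the consequences are possibilities. Nothing in the plan favours one handling of the unclassified eyes over another, the band-shift argument applies only if the five-year MD is used, and the MD distributions are assumed. All of this is correct. The true share could lie outside the illustrated range. The 84 eyes to be examined may also not be the denominator of the success rate, because section 2.2 adds patients from records alone.

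Fourth, the scope is narrow, and fixing the band on the preoperative MD has its own gap: section 2.4 allows a Humphrey or a TAP field before surgery, so some eyes may lack a Humphrey MD. Both points stand. The second calls for separate reporting of those eyes, not for leaving the band undefined.

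**Conclusion.** The concern holds. The rule is wrong as written: on either reading, some eligible eyes have no printed target, and on the only workable reading they are those with a loss of 5 dB or less. This follows from the text and needs no assumption. The number of eyes affected is unknown; 10% to 33% is an illustration that depends on the assumed MD distribution. No size or certain direction of bias in the success rate is claimed. Only the second classification is affected. The first classification, the IOP and medication outcomes and the sample size are not. The plan should be corrected before analysis.

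**What to change.** Reconcile sections 2.6 and 4.5 before the data are analysed.

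1. Restate the MD bands with consistent signs and limits so that every MD value falls in exactly one. The investigators should state, from the criteria they cite, which target applies to a loss of 5 dB or less; no value is proposed here.
2. State that the preoperative MD sets the band, so that progression after surgery cannot change an eye's own target.
3. Report how many eyes had a preoperative loss of 5 dB or less, and how many had no usable preoperative Humphrey MD.

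The cost is a few lines of text and no new examinations. The drawback is that eyes with only a TAP field, or with no preoperative field, need a stated rule and separate reporting; their number is not in the documents.
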